4. STATISTICAL ANALYSES

4.1. General Considerations

4.1.1. Immunogenicity

- GMC/GMT concentrations/titers below the assay cut-off will be given an arbitrary value of half the assay cut-off for the purpose of GMC/GMT calculation.
- The GMC/GMT calculations will be performed by taking the anti-log of the mean of the log concentration/titer transformations.
- Seroconversion rate for IPV neutralizing Ab is defined as percentage of participants with
 - Titer $\geq 1:8$ at 1 month after 3 dose primary schedule of IPV in participants who are seronegative before Dose 1 (titer $< 1:8$ pre-vaccination).
 - ≥ 4 -fold increase in titer 1 month after 3 dose primary vaccination schedule in participants who are seropositive before Dose 1 (titer $\geq 1:8$ pre-vaccination) after adjusting for maternal antibody decay assuming a half-life of 28 days.
- Seroconversion rate for *Rotarix* is defined as the percentage of participants who were initially seronegative (i.e., prior the first dose of *Rotarix*) and developed anti-RV IgA Ab concentration ≥ 20 U/mL 1 month post Dose 2.
- For a given participant and a given immunogenicity measurement time point, missing or non-evaluable measurements will not be replaced.

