
 To evaluate the reactogenicity of Rotarix PCV-free and IPV in terms of solicited systemic events. To assess the safety of Rotarix PCV-free in terms of unsolicited AEs and serious adverse events (SAEs) and safety of IPV in terms of SAEs. 	
 Solicited AEs 
 For each solicited systemic event, percentage of participants reporting the occurrence of the event within 14 days (Day 1- Day 14) after Dose 1 and Dose 2 of Rotarix and IPV Unsolicited AEs 
 Percentage of participants reporting the occurrence of unsolicited AEs within 31 days (Day 1- Day 31) after each dose of Rotarix, according to the MedDRA classification. SAEs: 
 Percentage of participants reporting SAEs from the first dose of the study intervention up to study end in the Co-administration and Staggered groups.

Ab: Antibody; GMC: Geometric mean Ab concentration; GMT: Geometric mean Ab titer; IgA: Immunoglobulin A; IPV: Inactivated poliovirus vaccine; MedDRA: Medical Dictionary for Regulatory Activities; mL: milliliter; PCV: *Porcine circovirus*; SAE: Serious Adverse Event; U: Unit

*Seroconversion rate for IPV neutralizing Ab is defined as percentage of participants with

- Titer $\geq 1:8$ at 1 month after 3 dose primary schedule of IPV in participants with titer $< 1:8$ pre-vaccination
- Titer ≥ 4 -fold increase in titer 1 month after 3 dose primary vaccination schedule in participants with titer $\geq 1:8$ pre-vaccination.

Note: the 4-fold increase will take into consideration the expected decline in maternal antibodies with estimated half-life of 28 days.

**Seroconversion rate for anti-RV IgA Ab is defined as the percentage of participants who were initially seronegative (i.e., with anti-RV IgA Ab concentration < 20 U/mL prior the first dose of *Rotarix*) and developed anti-RV IgA Ab concentration ≥ 20 U/mL at 1 month post Dose 2.

Refer to Section 8 for details on SAEs.

Refer to Section 9.3 and Section 9.4 for additional details on statistical analyses.

[figure not shown]
Details related to attributes of estimand covering intercurrent events, population and treatment definition are provided in the Section 9.

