8.1.4. Immunological correlates of protection

No recognized immunological correlate of protection (CoP) has been established for the antigen used as part of the HRV vaccine. However, an analysis by Cheuvart et al. in 2014 showed that post-vaccination anti-RV IgA seropositivity (Ab concentration ≥ 20 U/mL, measured by ELISA) is a correlate of vaccine efficacy in clinical trials of *Rotarix* [Cheuvart, 2014]. This was confirmed by an independent research group in 2020 [Baker, 2020].

Antibodies against poliovirus types 1, 2 and 3 will be determined by a virus microneutralization test adapted from the WHO Guidelines for WHO/EPI Collaborative Studies on Poliomyelitis [WHO position paper, 1993]. Titers will be expressed in terms of the reciprocal of the dilution resulting in 50% inhibition. The lowest dilution at which serum samples will be tested is 1:8. Antibody titers greater than or equal to 1:8 will be considered as protective.

The immunological assay results will be communicated to the investigator after the end of the study.

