9.3.2. Secondary immunogenicity endpoints analysis

The secondary endpoints are described in Section [3](#).

Anti-RV IgA Ab seroconversion rate and the percentage of participants with anti-RV IgA antibody concentration ≥ 90 U/mL at 1 month post Dose 2 of *Rotarix*; and the percentage of participants with poliovirus types 1, 2 and 3 neutralizing antibody titers $\geq 1:8$ and $\geq 1:64$ at 1 month post Dose 3 of IPV will be summarized by group with 95% CI.

For all antigens and timepoints as applicable, GMT/GMC will be computed with 95% CI. The 95% CI will assume that log transformed titer/concentration is normally distributed. For the purpose of GMT/GMC computation, titer/concentration below the assay cut-off will be assigned half of the cut-off.

For each of the anti-poliovirus types 1, 2 and 3, group GMT ratio at Visit 7 will be computed with 95% CI using an analysis of variance (ANOVA) model on log transformed titer in order to characterize the impact of co-administration on the IPV response. The group GMC ratio, the difference in seroconversion rates and the difference in the percentage of participants with concentration ≥ 90 U/mL will not be computed for anti-RV IgA antibody because a difference may be either attributed to co-administration of *Rotarix* PCV-free with IPV, or to the difference in administration schedule for *Rotarix* PCV-free (Month 0.5 and Month 1.5 in the Co-administration group, and Day 1 and Month 1 in the Staggered group).

Reverse cumulative curve will be provided for each antigen and timepoint as applicable.

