10.2. Appendix 2: Clinical laboratory tests

10.2.1. Protocol required immunogenicity laboratory assessments

Anti-RV IgA antibody determination:

The anti-RV antibody concentrations are determined by a validated anti-RV IgA ELISA. Microtiter plates (96-well) are coated with an anti-RV monoclonal antibody. The wells are washed and incubated with (positive wells) or without (negative wells) RV. Following incubation, the plates are washed and serum, standard and control dilutions are incubated in both types of wells (positive and negative). Bound anti-RV IgA in the wells are detected by incubation with peroxidase conjugated anti-human IgA polyclonal antibodies. Color development proportional to the quantity of bound anti-RV IgA occurs in the presence of a chromogen, TetraMethylBenzidine, and measured spectrophotometrically. Specific optical densities are calculated for each sample/control/standard dilution by measuring the difference between positive and negative wells, the use of negative wells allowing to assess non-specific IgA binding. The concentrations of the samples expressed in units per milliliter are calculated relative to the four-parameter logistic function generated from the standard curve.

Anti-IPV type 1, type 2 and type 3 antibodies determination:

The polio microneutralization assay measures neutralizing antibody titers to poliovirus types 1, 2, and 3 using 96-well microtiter plates. The principle of the test is that the anti-poliovirus antibodies in a serum sample will bind to the virus and block infection of susceptible cells. Because poliovirus is cytopathic, virus that is not bound by antibody infects and lyses cells. The amount of neutralizing antibody is quantitated as a titer based on the last serum dilution to protect susceptible cell culture wells from poliovirus infection and cytopathic effect.

10.3. Appendix 3: AE: definitions and procedures for recording, evaluating, follow-up, and reporting**10.3.1. Definition of an AE**

- An AE is any untoward medical occurrence in a clinical study participant, temporally associated with the use of a study intervention, whether or not considered related to the study intervention.
- Note: an AE can therefore be any unfavorable and unintended sign (including an abnormal laboratory finding), symptom, or disease (new or exacerbated) temporally associated with the use of a study intervention.

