4.2.1. Within groups assessment

The following calculations will be performed:

For each group, before Dose 1 and Visit 7 (1 month post Dose 3) time point,

- Seropositivity (before Dose 1 and Visit 7) and Seroconversion rates for IPV (at Visit 7) and their exact 95% confidence interval (CI) will be computed using the method of Clopper and Pearson [[Clopper](#), 1934],
- For participants who are seropositive before Dose 1 of IPV, the expected decline in maternal antibodies will be accounted for as follows. Assuming the maternal antibody half-life is 28 days, the estimated maternal antibody titer will be calculated as:

$$Titer(t) = titer(baseline) \times \exp\left(\frac{-\ln(2)}{t_{\frac{1}{2}}} \times t\right)$$

Where t is the time in days since baseline and $t_{\frac{1}{2}}$ is the expected half-life of the maternal antibodies of 28 days. The SAS code for calculating the adjusted titer is shown below:

```
data is_ipv;
  set is_ipv;

  if titer_prevaccination ge 8 then do;
    titer_adj= titer_prevaccination x exp((-ln(2)/28) x
    t));
    end;

  if titer_prevaccination < 8 then do;
    titer_adj=titer_prevaccination;
    end;
run;
```

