6.2.9. Immunogenicity data

- In general, the assay cut-off is the value under which there is no quantifiable result available. For an assay with a specific ‘assay cut_off’, the numerical immunogenicity result is derived from a character field (IS.ISSTRES):
 - if ISSTRES is ‘NEG’ or ‘-’ or ‘(-)’, numeric result= assay cut_off/2,
 - if ISSTRES is ‘POS’ or ‘+’ or ‘(+)’, numeric result = assay cut_off,
 - if ISSTRES is ‘< value’ and value<=assay cut_off, numeric result =assay cut_off/2,
 - if ISSTRES is ‘< value’ and value>assay cut_off, numeric result =value,
 - if ISSTRES is ‘> value’ and value<assay cut_off, numeric result =assay cut_off/2,
 - if ISSTRES is ‘> value’ and value>=assay cut_off, numeric result =value,
 - if ISSTRES is ‘<= value’ or ‘>= value’ and value<assay cut_off, numeric result =assay cut_off/2,
 - if ISSTRES is ‘<= value’ or ‘>= value’ and value>=assay cut_off, numeric result =value,
 - if ISSTRES is a value < assay cut_off, numeric result = assay cut_off/2,
 - if ISSTRES is a value >= assay cut_off, numeric result = ISSTRES
 - else numeric result is left blank.

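### The primary seroconversion rule sets no 1:8 minimum for baseline-seropositive infants, so an infant with baseline 1:8 and undetectable polio antibody after Dose 3 counts as a responder

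*SAP*

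**What the plan says.** Protocol Table 5 and SAP 1.1 and 4.1.1 define polio seroconversion in two branches. Infants below 1:8 before vaccination must reach 1:8 one month after the third IPV dose. Infants at or above 1:8 need a 4-fold "increase in titer 1 month after 3 dose primary vaccination schedule in participants who are seropositive before Dose 1", and the protocol adds that "the 4-fold increase will take into consideration the expected decline in maternal antibodies with estimated half-life of 28 days".

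SAP 4.2.1 carries this out: "For participants who are seropositive before Dose 1 of IPV, the expected decline in maternal antibodies will be accounted for as follows". It multiplies the baseline by an exponential decay factor to obtain titer_adj, with no lower bound. The SAS code stops there and does not derive the seroconversion flag.

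On the assay, protocol 8.1.4 states: "The lowest dilution at which serum samples will be tested is 1:8". It also states: "Antibody titers greater than or equal to 1:8 will be considered as protective".

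On results below the cut-off, SAP 6.2.9 derives the numeric result in general; for a less-than result the rule reads "value<=assay cut_off, numeric result =assay cut_off/2". Protocol 9.3.2 gives the same value for a narrower use: "For the purpose of GMT/GMC computation, titer/concentration below the assay cut-off will be assigned half of the cut-off". SAP 4.1.1 also links it to GMT/GMC.

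**The concern.** The package-insert definition used for the sample size (protocol 9.7) needs an unadjusted 4-fold rise from at least 1:8, so a responder has at least 1:32. The decay adjustment removes that built-in minimum and nothing replaces it. By the final blood sample the adjusted baseline of a low-seropositive infant is below 1, and four times that value lies below the lowest dilution tested.

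An infant who starts at 1:8 and ends with no detectable antibody is then a seroconverter, while a seronegative infant with the same final result is not. The three polio seroconversion rates are the whole of the confirmatory objective. Calling unprotected infants responders can hide part of a true deficit. It can also shift the arms unequally, because the Staggered baseline sample is drawn about 15 days earlier.

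**Working it through.** **The plan's own figure.** Inputs from protocol 9.7 and SAP 5: rates 96.23%, 93.83% and 97.60%, true difference 0, 160 evaluable per arm, margin -10 points, one-sided 0.025. The stated powers are 98.2%, 92.5% and 99.7%, and 100 - (1.8 + 7.5 + 0.3) = 90.4% overall, as printed. Exact binomial enumeration with the Miettinen-Nurminen score limit gives 98.6%, 93.8% and 99.8%, overall 92.1%. The figures agree within 2 points.

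**Intervals from baseline to Visit 7** (protocol Tables 3, 4 and 8).
- Co-administration, Visit 2 to Visit 7: optimal 30 + 30 + 30 = 90 days; allowed 28 + 28 + 30 = 86 to 3 x 36 = 108.
- Staggered, Visit 1 to Visit 7: optimal 15 + 30 + 30 + 30 = 105 days; allowed 14 + 28 + 28 + 30 = 100 to 18 + 3 x 36 = 126.

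**Required titre.** For baseline B it is 4 x B x 2^(-t/28).

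| t (days) | 2^(-t/28) | Required when B = 8 | Fold rise if result is coded 4 |
|---|---|---|---|
| 86 | 0.1190 | 3.81 | 4.20 |
| 90 | 0.1077 | 3.45 | 4.64 |
| 105 | 0.0743 | 2.38 | 6.73 |
| 126 | 0.0442 | 1.41 | 11.31 |

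Break-even for B = 8 is t = 84 days, shorter than any allowed interval, so a coded 4 always passes.

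**Which baselines are affected.** A coded 4 passes when B is at most 2^(t/28): 9.3 at 90 days and 13.4 at 105 days. With two-fold titres that means 1:8 in both arms, plus 1:16 in the Staggered group from 112 days (4 x 16 x 0.0625 = 4.00), an interval the Co-administration windows do not reach. The required titre is below 8 for B up to 2 x 2^(t/28): 18.6 and 26.9.

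**Effect on the comparison.** The documents give no maternal titre distribution. Assumptions:
- log-normal titres at Visit 1, median 4 to 32, SD 1.5 to 2 on the log2 scale;
- true decay with a 28-day half-life, so the Co-administration mean is 15/28 log2 lower at its baseline;
- non-response independent of baseline.

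The table shows the share of complete non-responders (undetectable after Dose 3) who are counted as converted.

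| Titre scale | Staggered | Co-administration |
|---|---|---|
| Continuous | 11-19% | 3-6% |
| Two-fold, rounded down | 15-25% | 11-26% |

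On the two-fold scale the order of the arms reverses between medians 8 and 16.

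*No true difference.* If every planned non-converter is a complete non-responder (the upper bound), the continuous scale shifts the difference by -0.2 to -0.9 points and overall power falls from 92.1% to 89.5-91.1%. If half are, the shift is -0.1 to -0.4 points. On the two-fold scale the upper-bound shift is -0.3 to +0.3 points.

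*True deficit of 10 points under the rule with the 1:8 minimum, two-fold scale.* Worked case: type 3, median 16, SD 1.5, all non-converters undetectable. Staggered is 0.976 + 0.024 x 0.248 = 0.982. Co-administration is 0.876 + 0.124 x 0.261 = 0.908. The apparent deficit is 7.4 points, and the chance of passing for that type is 14.1%, against 2.2% without masking. Across the assumed range:

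| Non-converters who are undetectable | Chance of passing, one type |
|---|---|
| none counted as converted | 2.2-2.4% |
| 10% | 2.4-2.9% |
| 25% | 2.6-3.7% |
| 50% | 3.1-5.9% |
| 100% | 3.9-14.1% |

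The apparent deficit is 7.3-9.3 points at 100% and 8.7-9.6 points at 50%. On the continuous scale the chance is 1.9-2.6% even at 100%. These are single-type figures; they bound the overall risk when the other two types pass.

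**The case against.** The strongest reply concerns weight.

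- **Error against which definition?** The 14.1% is not type I error of the planned test, because the null hypothesis is framed on the plan's own seroconversion rate. It is error measured against the rule with the 1:8 minimum. That is correct and should be said whenever the figure is used.
- **Conjunction of assumptions.** The figure needs a deficit at the margin, every non-converter undetectable after three doses, two-fold titres and a near-worst maternal distribution. At 10% or 25% undetectable the inflation is slight.
- **Titre scale.** Protocol 8.1.4 describes a 50% inhibition titre, which reads as continuous. Protocol 10.2.1 says the antibody is "quantitated as a titer based on the last serum dilution to protect susceptible cell culture wells", which suggests two-fold steps. The direction is therefore open: on the continuous reading the effect works against concluding non-inferiority.
- **Existing check.** SAP 4.3.1 and 4.3.2 report the percentages at or above 1:8 and their between-group interval, where these infants count as failures. That comparison is descriptive, however, and the sensitivity analyses in SAP 4.2.3 change the analysis set or subgroup, never the definition.
- **Half the cut-off may be for GMTs only.** If so, the plan gives no value for a sub-cut-off result in the fold rise, and the outcome is undefined for baselines up to 18.6 and 26.9. If SAP 6.2.9 governs, the wrong call is confined to the narrower band up to 9.3 and 13.4. Either reading needs a sentence.

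None of this touches the basic arithmetic.

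**Conclusion.** The concern holds. Followed as written, with the SAP 6.2.9 coding, the primary rule classes an infant with baseline 1:8 and undetectable antibody after Dose 3 as seroconverted in both arms at every per-protocol interval. That conclusion needs no outside assumption.

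The effect on the trial result is probably small: under one point with no true difference, and little or much less than the 14.1% bound at a true 10-point deficit unless most non-converters are undetectable and titres move in two-fold steps. Those sizes rest on the assumed maternal distribution, 28-day decay and independence of non-response from baseline. The point should be corrected because the fault lies in the definition of the only confirmatory endpoint, not because a large bias has been shown.

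**What to change.** In Protocol Table 5 and SAP 1.1, 4.1.1 and 4.2.1, define seroconversion for baseline-seropositive infants as a post-Dose 3 titre of at least 1:8 and at least 4 x titer_adj. State that a result below 1:8 is never a seroconversion, whatever number SAP 6.2.9 assigns to it, and say whether half the cut-off applies outside GMT/GMC. Add the derivation of the flag to the SAS code. If the primary definition can no longer change, pre-specify this rule in SAP 4.2.3 as a sensitivity analysis of the primary between-group comparison.

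The cost is a change of wording to the confirmatory endpoint in both documents and one condition in code; no new data are needed. Because the trial is open-label, it should be settled before serology results are available. Rates may fall slightly. The worst-case argument in protocol 9.7 still holds, since an unadjusted 4-fold rise from at least 1:8 is at least 1:32 and meets both conditions. At the optimal intervals nothing changes from baseline 1:32 upward (required titres 13.8 and 9.5). The minimum does not remove every effect of the different baseline visits: the arms share the same threshold only if decay follows the assumed half-life and titres are continuous.

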4.1.2. Reactogenicity

Participants without events (solicited/unsolicited AEs or concomitant medications) reported will be treated as participants without the events (solicited/unsolicited AEs or concomitant medications, respectively).

Refer to Section 6.2.4.2 for the intensity grading of solicited AEs.

4.2. Primary Endpoint(s) Analyses

Analyses on the immunogenicity endpoint will be conducted primarily on the Per Protocol Set.

4.2.1. Within groups assessment

The following calculations will be performed:

For each group, before Dose 1 and Visit 7 (1 month post Dose 3) time point,

- Seropositivity (before Dose 1 and Visit 7) and Seroconversion rates for IPV (at Visit 7) and their exact 95% confidence interval (CI) will be computed using the method of Clopper and Pearson [[Clopper](#), 1934],
- For participants who are seropositive before Dose 1 of IPV, the expected decline in maternal antibodies will be accounted for as follows. Assuming the maternal antibody half-life is 28 days, the estimated maternal antibody titer will be calculated as:

$$Titer(t) = titer(baseline) \times \exp\left(\frac{-\ln(2)}{t_{\frac{1}{2}}} \times t\right)$$

Where t is the time in days since baseline and $t_{\frac{1}{2}}$ is the expected half-life of the maternal antibodies of 28 days. The SAS code for calculating the adjusted titer is shown below:

```
data is_ipv;
  set is_ipv;

  if titer_prevaccination ge 8 then do;
    titer_adj= titer_prevaccination x exp((-ln(2)/28) x
    t));
    end;

  if titer_prevaccination < 8 then do;
    titer_adj=titer_prevaccination;
    end;
run;
```

4.2.2. Between groups assessment

The asymptotic standardized 95% CI for the difference in seroconversion rate for IPV at Visit 7 between Co-administration group minus staggered group will be computed using the method of Miettinen and Nurminen [[Miettinen](#), 1985]

4.2.3. Sensitivity analyses

If more than 5% of the ES participants with immunogenicity results after study intervention are excluded from the PPS, the confirmatory analysis will be repeated on the ES.

Within groups assessment for the PPS will be repeated by sex and study sites.

4.3. Secondary Endpoint(s) Analyses

Refer to Section [4.5](#) for safety analyses.

Analyses on the immunogenicity endpoints will be conducted primarily on the PPS.

4.3.1. Within groups assessment

The following calculations will be performed:

For each group, 1 month post Dose 2 for *Rotarix* PCV-free and 1 month post Dose 3 for IPV timepoint,

- Seropositivity (before Dose 1 and 1 month post Dose 2) and Seroconversion rates for *Rotarix* PCV-free (1 month post Dose 2) and their exact 95% confidence interval (CI) will be computed using the method of Clopper and Pearson [[Clopper](#), 1934],
- GMCs/GMTs were applicable and their exact 95% CIs will be computed.
- The percentage of participants with anti-poliovirus 1, 2, and 3 neutralizing Ab titers $\geq 1:8$ and $\geq 1:64$ and their exact 95% CI for each group at 1 month post Dose 3 will be computed.
- The percentage of participants with anti-RV IgA antibody concentrations ≥ 90 U/mL and their exact 95% CI for each group at 1 month post Dose 2 will be computed.
- The distribution of anti-RV IgA Ab concentrations 1 month post Dose 2 and anti-poliovirus titers 1 month post Dose 3 will be displayed using reverse cumulative curves for the PPS

4.3.2. Between group assessment

- The asymptotic standardize 95% CI for the difference in the percentage of participants with anti-poliovirus types 1, 2 and 3 neutralizing Ab titers $\geq 1:8$ and $\geq 1:64$ at Visit 7 between Co-administration group minus staggered group will be computed.
- The 95% CI for the ratio of anti-poliovirus type 1, 2 and 3 Ab GMTs at Visit 7 between Co-administration group over staggered group will be computed.

